1.0 Research Introduction

1.1 Purpose/Specific Aims

This study will test the feasibility and acceptability of a telehealth-delivered treatment designed to help smokers with serious mental illness to quit using a therapy approach focused on increasing task persistence.

A. Objectives

We will test the feasibility, acceptability, and initial efficacy of our PTSC-S intervention when delivered via telehealth.

B. Hypotheses / Research Question(s)

1. We hypothesize that the PTSC-S intervention will be acceptable to participants, and the study will be feasible to conduct.
2. As compared to baseline, participants will report greater task persistence as evidenced by reduced scores on the Thoughts About Smoking Questionnaire (TASQ).
3. As compared to baseline, participants will report smoking fewer cigarettes per day at 1- and 3-month follow-up.

1.2 Research Significance (Briefly describe the following in 500 words or less):

We created a treatment manual designed to help smokers with serious mental illness to quit smoking, in part, by targeting deficits in the tendency to persist in difficult or frustrating tasks (i.e., "task persistence"). While several measures of task persistence were not found to be significantly changed in the study, we detected a significant change (in the hypothesized direction) on a measure of thoughts likely to dampen task persistence as it relates to. Specifically, as hypothesized, scores on the Thoughts About Smoking Questionnaire (TASQ) showed significant decreases from baseline to the target quit date, $t(16) = 7.753$, $p < 0.001$, and maintained those significant decreases from baseline to end-of-treatment, $t(19) = 4.537$, $p < 0.001$.

In addition, we found that the intervention was feasible and understandable. Once we began providing transportation to our research participants, attendance exceeded our goal of 65% of participants attending at least 6 of 8 treatment sessions. We also found that in response to the statement, "Overall, this treatment was easy to understand," 68.8% of participants endorsed "7: Totally Agree" with an additional 18.8% endorsing "6: Agree very much" for a total of 87.6% endorsing at least a 6 out of 7. In response to the statement, "Overall, this treatment was helpful," 56.3% of participants endorsed "Totally Agree" with an additional 25% endorsing "Agree very much" for a total of 81.3% endorsing at least a 6 of 7.

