1.3 Research Design and Methods

Overview: We will evaluate the feasibility and acceptability of our intervention (Persistence Targeted Smoking Cessation for Serious Mental Illness; PTSC-S) when delivered via telehealth in a single group, within-subjects design.. The purpose of this trial is to test the feasibility, acceptability, and initial efficacy of our PTSC-S intervention.

A. Participant Recruiting and Screening: The project will take place remotely via telehealth to reduce patient burden and travel difficulties. Our Rutgers offices in New Brunswick, NJ, are located in the building next to a large University Behavioral Health Care outpatient clinic that serves clients with serious and persistent mental illness. We will recruit New Jersey resident smokers from Rutgers University Behavioral Health Care, from the community via our website, social media, and local flyers, via Rutgers listservs, local

agencies or organizations who serve mental health consumers (i.e. CHOICES; Serv Behavioral Health Systems, Inc.; George J. Otlowski, Sr. Center for Mental Health Care, Hunterdon Behavioral Health Care), and ElevateU's Study Recruitment Platform (more detailed information listed below under "ElevateU Recruitment"). We will use IRB approved language from recruitment advertisements for electronic communication (i.e. listservs, newsletters, ect.) with approved study sites. Potential participants will call our offices for a telephone pre-screen or fill out an interest form on Qualtrics that would be followed by a telephone pre-screen. If potentially eligible, they will be offered a more in-depth telehealth phone or video assisted screening after providing informed consent. If all inclusion criteria are met, they will be invited to participate. This is an urban area with a large low-income population and therefore a greater proportion of smokers than the average of 14.8% in the state of New Jersey. Previous studies have given us the necessary experience with Rutgers listservs, websites, Craigslist, and use of flyers and brochures to maximize recruitment.

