1.6 Study Variables

A. Independent Variables, Interventions, or Predictor Variables

We will provide 8-weeks of free telehealth counseling to participants and 10 weeks of nicotine transdermal patch (an FDA-approved, over-the-counter medication).

“Persistence-Targeted Smoking Cessation in those with Serious Mental Illness (PTSC-S)” is an 8-session, individual, smoking cessation counseling strategy that focuses heavily on using cognitive behavioral therapy targeted at disputing automatic thoughts that may reduce task persistence for smokers with serious mental illness. While disputing automatic thoughts will be the focus of each session, skill building and support will also be included. Participants will be asked to complete homework assignments between sessions – including keeping a daily thought record to monitor automatic thoughts that may put them at risk for smoking. A daily thought record is a commonly used cognitive behavioral therapy homework assignment in which participants practice identifying and evaluating their thoughts. Participants will also track their daily cigarette use and nicotine patch use for homework.

We will give participants a 10-week supply of the nicotine transdermal patch (an FDA-approved, over-the-counter medication) to be used starting two weeks prior to their Quit Date. Although the nicotine patch is commercially available without a doctor’s prescription, Co-I [name] (an addiction psychiatrist) will provide medical monitoring during this study. Consistent with the product insert, participants will be instructed to use one nicotine patch daily, and to apply it upon awakening at about the same time each day. Subjects will be instructed to vary the site of application of the patch daily to minimize any skin irritation. They will use the 21mg patch for the first 8-weeks, then 2-weeks of the 14mg patch.

B. Dependent Variables or Outcome Measures

Primary Outcome measures

- We will measure prolonged abstinence with a 2-week grace period following the target quit date until end-of-treatment and 3-months post quit-date

- We will measure feasibility using a scale regarding how “useful” the intervention was, how acceptable the length of each session was, and how acceptable the number of counseling sessions offered was (with higher scores reflecting ratings of more useful and more acceptable).
- Follow-up rates of at least 80% at the 3-month follow-up
- Rates of missing/unusable data will be < 10% of all data collected

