4.2 Subject Selection and Enrollment Considerations

A. Recruitment Details

Research assistants will post flyers at UBHC and will work with staff for help in connecting with potential participants. Research assistants will post flyers and place leaflets in local areas.

B. Source of Subjects

We will recruit smokers from Rutgers University Behavioral Health Care, from the community via our website and local flyers, via social media, via Rutgers listservs, local agencies or organizations who serve mental health consumers (i.e. CHOICES, SERV Behavioral Health Systems, Inc.; George J. Otlowski, Sr. Center for Mental Health Care, Hunterdon Behavioral Health Care), and ElevateU's Study Recruitment Platform (explained above in section 1.3 1.3 Research Design and Methods).

C. Method to Identify Potential Subjects

Participants responding to flyers or otherwise referred will complete a telephone screen to determine likely eligibility. If potentially eligible, they will be offered a more in-depth telehealth appointment screening after providing informed consent. If all inclusion criteria are met, they will be invited to participate.

D. Subject Screening

Interested participants will complete a brief telephone screening where they will be assessed by trained study personnel who will determine initial eligibility.

Inclusion Criteria

- Must be between 18 – 70 years old
- Must indicate willingness to make a quit attempt in the next 30 days
- Must report being a daily smoker (including those labeled “little cigars”) for past month
- Must have a diagnosis of Schizophrenia, Schizoaffective Disorder, or Bipolar Disorder on SCID-5-RV
- Psychiatric illness must be stable, as indicated by no hospitalizations in previous 8 weeks, and a stable psychotropic medication regimen for 8 weeks

- Must have a smartphone, tablet, or computer with ability to download apps
- Must currently receive mental health treatment
- Must sign release of information for current mental health treatment providers

Exclusion Criteria

- Must not currently (in past 10 days) be taking varenicline (Chantix),
- Must not currently (in past 10 days) be taking bupropion (Zyban/Wellbutrin) to quit smoking.
- Must not be taking any nicotine preparations (gum, lozenge, patch, spray, inhaler) daily over the last 10 days
- Must not be currently receiving tobacco dependence treatment counseling.

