4.3 Subject Randomization

N/A

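### The stated aim of testing initial efficacy of PTSC-S goes beyond what a single-group, before-and-after design with universal nicotine patch can show

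*Combined protocol and SAP*

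**What the plan says.** **Aim.** Section 1.1 A: "We will test the feasibility, acceptability, and initial efficacy of our PTSC-S intervention when delivered via telehealth". Section 1.3 names the same three aims as the trial's purpose.

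**Design.** Section 1.3 describes evaluation "when delivered via telehealth in a single group, within-subjects design". Section 4.3 (randomization) is marked not applicable.

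**What PTSC-S is.** Section 1.6 A says it "is an 8-session, individual, smoking cessation counseling strategy". The patch is described separately in the same section: "We will give participants a 10-week supply of the nicotine transdermal patch", to be used from two weeks before the quit date.

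**Who enters.** Section 4.2 D: "Must indicate willingness to make a quit attempt in the next 30 days" and "Must report being a daily smoker".

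**Tests.** Section 6.1 A gives one-tailed paired t-tests against baseline for the Thoughts About Smoking Questionnaire (TASQ; Hypothesis 2) and cigarettes per day (Hypothesis 3). Prolonged abstinence is a primary outcome in 1.6 B, but 6.1 gives no analysis or external benchmark for it.

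**Language around the tests.** Sections 1.5 and 6.1 B describe the pilot's baseline-to-follow-up dz of 1.28 as an effect of the intervention. Section 6.3 G plans to compare adverse events between treatment groups. Section 6.3 H allows the trial to stop if PTSC-S proves superior to a control intervention.

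**The concern.** Efficacy of PTSC-S means what the counselling adds. The paired t-test's null is zero mean change from baseline, whatever the cause. Four other sources of change run alongside the counselling in every participant: an active cessation drug, a planned quit attempt, the passage of time and repeated testing. With no group that has these without PTSC-S, the data cannot separate them.

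The problem is most direct for cigarettes per day, because the patch and the quit attempt act on smoking itself. TASQ is closer to what the counselling targets. It is still an investigator-developed self-report scale (1.9), completed by people who are trying to quit, so quit intention and repeat testing can move it too.

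What is at stake is the conclusion the trial may draw. No section limits the causal reading of a before-and-after change, and section 1.4 already draws that reading from pilot changes: it concludes that PTSC-S influenced its target mechanism. Section 6.4 foresees publications and grant applications.

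**Working it through.** **Inputs.** dz = 0.5, alpha 0.05, power 80%, N = 27, 20% loss, 34 recruited, and baseline values imputed where follow-up is missing (1.5 and 6.1 B). One-tailed paired t-test (6.1 A).

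**Step 1: reproduce the plan's figures.** Power = P(T > t(0.95, n − 1)), where T is noncentral t with n − 1 degrees of freedom and noncentrality dz × √n.
- dz = 0.5, n = 27: critical t = 1.706, noncentrality 0.5 × √27 = 2.60, power 81.2%. At n = 26 power is 79.8%, so 27 is the smallest adequate number.
- dz = 1.28, n = 6: power 85.0%. At n = 5 it is 75.8%.
- Recruitment: 27 / 0.8 = 33.75, rounded up to 34.

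All three stated figures reproduce as one-sided exact calculations. The arithmetic is sound. It gives power to detect any mean fall from baseline, because dz is a within-person change and not a difference from a control.

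**Step 2: suppose PTSC-S adds nothing.** Let the patch, quit attempt and time together produce a change of size dz. The documents give no figure for this, so a range is shown. The chance of a significant one-tailed test is:

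| Assumed dz from other causes | 27 completers | 27 observed + 7 imputed at baseline |
|---|---|---|
| 0.1 | 13% | 13% |
| 0.2 | 26% | 26% |
| 0.3 | 45% | 45% |
| 0.4 | 65% | 65% |
| 0.5 | 81% | 81% |

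The first column uses the formula in step 1. The second is a simulation of normal changes in 27 people plus seven zeros, tested with 33 degrees of freedom. The seven zeros shrink the mean and the standard error almost equally, so the imputation barely changes the result.

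**Step 3: sensitivity to the sample size.** Sections 4.1 and 4.5 C give 61 participants instead. With 61 observed changes, dz of 0.3 to 0.5 gives 75% to 99%. With all 34 recruits observed and no loss, it gives 53% to 89%. A larger sample makes a significant result more likely but does nothing for attribution.

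**Step 4: set the sections side by side.** Sections 1.1 A and 1.3 claim efficacy of the counselling. Section 1.3 also specifies evaluation "in a single group, within-subjects design", and the test in 6.1 A addresses change under counselling plus patch in people ready to quit. Sections 6.3 G and H presuppose a comparison group that 1.3 and 4.3 rule out.

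**The case against.** The best defence is that the operative hypotheses do not overreach. Hypotheses 2 and 3 are framed as comparisons with baseline and attribute nothing. The opening sentences of 1.1 and 1.3 name only feasibility and acceptability, the word initial is a hedge, and the patch is openly listed with the counselling. A single group suits those aims. All of this stands, and it confines the fault to the efficacy label and the related effect language. But initial conveys an early stage; it does not supply a comparator.

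Two further defences carry some weight. TASQ targets the cognitions that the counselling addresses, and 1.4 reports that several other persistence measures did not change in the pilot, which is some evidence against a generic shift over time. It is not decisive, since quit intention could move thoughts about smoking without moving those measures. Baseline imputation is cautious about dropout but does not address attribution.

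A reader might infer more than the documents support:
- *That the plan commits to reporting a significant Hypothesis 2 or 3 as efficacy of the counselling.* No section says so; 6.4 says only that aggregate results may be reported.
- *That the 45% to 81% is an inflated type I error, to be set against 5%.* It is not. If the patch lowers smoking, Hypothesis 3 as written is true and detecting the fall is power.
- *That a control arm is required.* The feasibility and acceptability aims do not need one.

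**Conclusion.** Wrong as written, in the claim and not in the sample-size arithmetic or the choice of a single group. Sections 1.1 A and 1.3 promise a test of something the design cannot isolate, and no section restrains the reading. If other causes produce dz of 0.3 to 0.5, an efficacy reading would be triggered about 45% to 81% of the time when PTSC-S adds nothing. Those percentages rest on the assumed dz range, normally distributed changes, and 27 completers with or without seven baseline-imputed participants. The conclusion itself does not depend on the range: any non-zero fall from other causes raises the chance of a significant test without involving the counselling. The point is strongest for cigarettes per day and weaker, though not absent, for TASQ.

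**What to change.** 1. In 1.1 A and 1.3, replace the initial-efficacy wording with: *change from baseline in smokers receiving PTSC-S by telehealth plus nicotine patch*.
2. In 6.1, state that Hypotheses 2 and 3 estimate pre-post change, reported with confidence intervals, and will not be interpreted as an effect of PTSC-S.
3. In 1.5 and 6.1 B, describe the pilot dz as a pre-post change and not as an effect of the intervention.
4. Reconcile 6.3 G (treatment groups) and 6.3 H (control intervention) with the single-group design in 1.3 and 4.3.

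The cost is protocol wording only, with no added participants or procedures. The downside is a less favourable claim.

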1.3 Research Design and Methods

Overview: We will evaluate the feasibility and acceptability of our intervention (Persistence Targeted Smoking Cessation for Serious Mental Illness; PTSC-S) when delivered via telehealth in a single group, within-subjects design.. The purpose of this trial is to test the feasibility, acceptability, and initial efficacy of our PTSC-S intervention.

A. Participant Recruiting and Screening: The project will take place remotely via telehealth to reduce patient burden and travel difficulties. Our Rutgers offices in New Brunswick, NJ, are located in the building next to a large University Behavioral Health Care outpatient clinic that serves clients with serious and persistent mental illness. We will recruit New Jersey resident smokers from Rutgers University Behavioral Health Care, from the community via our website, social media, and local flyers, via Rutgers listservs, local

agencies or organizations who serve mental health consumers (i.e. CHOICES; Serv Behavioral Health Systems, Inc.; George J. Otlowski, Sr. Center for Mental Health Care, Hunterdon Behavioral Health Care), and ElevateU's Study Recruitment Platform (more detailed information listed below under "ElevateU Recruitment"). We will use IRB approved language from recruitment advertisements for electronic communication (i.e. listservs, newsletters, ect.) with approved study sites. Potential participants will call our offices for a telephone pre-screen or fill out an interest form on Qualtrics that would be followed by a telephone pre-screen. If potentially eligible, they will be offered a more in-depth telehealth phone or video assisted screening after providing informed consent. If all inclusion criteria are met, they will be invited to participate. This is an urban area with a large low-income population and therefore a greater proportion of smokers than the average of 14.8% in the state of New Jersey. Previous studies have given us the necessary experience with Rutgers listservs, websites, Craigslist, and use of flyers and brochures to maximize recruitment.

ElevateU. ElevateU is a pilot recruitment platform funded by the National Institute on Drug Abuse. The purpose of the online platform is to match individuals with substance use disorders who wish to participate in research with researchers doing relevant substance use research. The recruitment platform is currently in a pilot phase and there is therefore no fee or contractual agreement related to using this National Institute on Drug Abuse funded platform.

Access to ElevateU's recruitment platform <https://moshemu.com/> is provided to researchers at no cost. Researchers may register and create an entry describing their research study on the Moshemu website for potentially interested individuals to view. ElevateU advertises online, at no cost to the research teams for research studies. Potential research participants who see the advertisement may choose to click on the advertisement link which will take them to a description of the study. If interested in that study, the potential research participant can "sign up" to be contacted by the research team via email and/or phone numbers.

ElevateU, as part of this registration process, potential research participants may choose to voluntarily provide information related to health behaviors so they can be contacted in the future if they match with other relevant research studies. Providing this information is voluntary. The ElevateU platform is seen as providing minimal risk to participants who wish to enroll in studies because the website and registration/data storage process is similar to methods currently being used in people's day to day lives. For example, people typically register on Facebook, Reddit, and online patient communities such as "Patients Like Me," where they provide information about their health either through free text conversations and/or responses to questions. This website will be using similar methods and therefore seen as minimal risk to participants.

Furthermore, the primary method of identification will not be through name but through email address. Participants have the ability to create a new email address by creating a free email through tools such as gmail.com. Overall, we believe these methods involve minimal risk and have been used in a variety of IRB-approved studies by our team (e.g., UCLA and UC Irvine researchers) in the past.

All information collected via ElevateU's platform will be stored in an encrypted database. Two copies of the encryptions will be created with a passkey for each user (participant on the online recruitment platform) and for each study that the user enrolls in. If the user opts into the study, a copy of their data becomes encrypted with a passkey of the study. It is therefore will only ever be accessible to the user themselves and to the manager of any study they enroll in.

Recruitment using ElevateU. ElevateU will advertise, at no cost to us, for the IRB approved study, Persist to Quit: Telehealth Counseling for Smokers with Serious Mental Illness. Information about our IRB approved study will only be described in language consistent with already IRB approved study flyers. As noted above, potential participants who see the advertisement will have the option to click the link on the ad, read about the study, and opt-in to being contacted by IRB approved research staff if they are interested in participating or learning more about our study.

When a potential participant actively opts-in to being contacted, [name] account will be notified. The research team will then have access to the contact information the potential participant chose to provide. [name] team will be able to download a CSV file with the contact information and [name] will store this file on the secure HIPAA compliant Rutgers OneDrive folder.

Study Procedures: A trained research assistant (who will receive weekly and as-needed supervision from the principal investigator) will pre-screen potential participants on the phone, followed by a pre-baseline tutorial regarding the required technology and assist with any troubleshooting needs. A research assistant will meet with participants via telephone or telehealth video platform, obtain informed consent via a HIPAA compatible survey platform (i.e., Red Cap or Qualtrics), and administer the baseline assessment battery (see Assessment Measures table below). We will divide the baseline assessment battery into two sessions to minimize participant fatigue if necessary. Each baseline assessment session will last approximately 90 minutes.

The research coordinator (who will receive weekly and as-needed supervision from the principal investigator) will screen participants at baseline using the SCID-RV for suicide risk exclusion criteria. If any participant indicates high levels of depression or suicidality, we will provide phone numbers and a recommendation to contact Rutgers University Behavioral Health Care or the Rutgers RWJMS Department of Psychiatry outpatient practice. In case of imminent suicide risk, a research staff member will call Acute Psychiatric Services (APS) at [contact] with the research participant and the principal investigator will be contacted immediately.

Questionnaires that are commonly used in tobacco dependence treatment studies will be used in the current study. Women of childbearing age will confirm in writing that they are not pregnant or nursing, not planning on becoming pregnant in the next three months, and that they are using effective birth control if they are sexually active. Carbon monoxide (CO) levels (also commonly collected in tobacco dependence treatment studies) will be assessed with a personal carbon monoxide monitor that connects to one's mobile device and CO reading in parts per million (ppm) will be recorded.

Study Intervention: We will provide free, weekly individual telehealth video counseling sessions for 8 weeks and 10-weeks' worth of the nicotine transdermal patch (an FDA-approved smoking cessation product available over the counter). All sessions will be video recorded for treatment integrity and supervision.

HIPAA compatible video platform: We will use Microsoft Teams for all assessment and telehealth counseling appointments. If there are any problems connecting to Microsoft Teams, we will use Doxy.me or Zoom as a backup. Both Microsoft Teams, Doxy.me, and zoom are HIPAA compatible platforms for telehealth services. A trained research assistant will meet with each participant via Microsoft Teams (or via telephone) if participant is unable to use the technology without any assistance

to review technology, telehealth application, and assist with any technology issues prior to the beginning of assessment or counseling.

In the event we are unable to meet with a patient using telehealth video services (e.g. because of internet connectivity issues), we will provide counseling using the telephone. There is a strong literature supporting tobacco "QuitLines", proactive telephone counseling and we would therefore still be providing treatment via an empirically supported format. We expect this will in the best interest of the patient as abruptly stopping treatment would be unethical.

Emails: We may create a Google account email with a complex password for each research participant using their assigned ID number and short title of our study "ptscs" (i.e. ID#[contact]) if a participant does not have an email address to use. We will store this information using the HIPAA compliant Microsoft OneDrive cloud storage system and may assist participants with their email as needed. No PHI will be transmitted via this email account. This email will be used to set up the Smokerlyzer application for the iCO Smokerlyzer device, as the application requires an email to be sent to our research team with the results of their breath test. We will ask our participants to not use this email account for communication outside of the research study to protect their confidentiality. See section 1.7.2 for more on the iCO Smokerlyzer device.

- B. Data Points:** We will collect data at baseline, at the end of treatment, and at follow up at 3-months post quit date.
- C. Duration:** Participants will be active in the study for approximately 4 months. We anticipate completing data collection activities within 32 months.
- D. Primary study endpoints** include baseline, at the end of treatment, and at follow up at 3-months post quit date. We will assess AEs on a rolling basis and report them at DSMB meetings. We will conduct an interim analysis after 50% of the target enrollment has completed followup assessment.

